A major reason for this is that no currently available allergy test can accurately identify specific food triggers leading to EoE. For example, two studies have shown that an elimination diet based on skin-prick testing correctly identifies food triggers in only 13%, a rate that is far worse than expected by chance alone.^{17, 22} Because of this, successful dietary therapy requires empiric elimination of a large number of foods, subsequent reintroduction of single foods, then endoscopy and biopsy to assess for recurrent tissue eosinophilia.⁵ This leads to dietary changes that are frequently unnecessary, and the serial endoscopies, which can number up to 10 in a single year,²² are costly and risky.³ Finally, while alternative treatment with topical corticosteroids is possible in patients who cannot comply with dietary therapy, not all patients respond, and long-term use of this medication class is unsafe.^{23, 24} Therefore, there is a critical need to develop methods to reliably identify allergen triggers. This will advance understanding of the biology of EoE, lead to substantially improved therapy, and reduce costs.

This study uses novel and highly innovative techniques to identify dietary triggers and individualize dietary treatment regimens, making dietary elimination practical and more palatable

A novel allergen-specific immune signature-directed approach to food trigger identification has great promise for EoE. The current model of EoE pathogenesis holds that when food antigens are presented to the GI tract, either in the esophagus or in the small intestine, previously sensitized T cells are triggered to produce a cascade of Th2 cytokines, including IL-4, IL-5, and IL-13.⁸ In addition, a recent study has identified food-specific IgG4 as important to the pathogenesis.¹² Because this model is neither simply an immediate IgE- nor a classic delayed IgG-mediated response, it is not surprising that skin prick or patch tests are not accurate.

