|-------------------|--------|-----------------------|----------------------|---------|
| | | | | |
| Total | | 1847 | 469 | 0.008 |
| Peanut | | 4.05 | 0.01 | 0.003 |
| Soy | | 2.12 | 0.01 | < 0.001 |
| Egg | | 61.4 | 2.88 | < 0.001 |
| Milk | | 55.8 | 0.67 | < 0.001 |
| Wheat | | 19.9 | 1.10 | < 0.001 |

[figure not shown]

Table 2: [REDACTED] performance of esophageal IgG4 for identifying food triggers in EoE

| | Nut | Egg | Soy | Wheat | Milk |
|------------------------|-----|-----|-----|-------|------|
| Testing parameters (%) | | | | | |
| Sensitivity | 0 | 88 | 0 | 60 | 55 |
| Specificity | 80 | 75 | 100 | 100 | 100 |
| Agreement | 67 | 80 | 67 | 77 | 53 |

The second allergen-specific signature we assessed was the lymphocyte proliferation assay developed by the investigators. Here, investigators again used the sub-population of EoE patients who successfully responded to dietary elimination and in whom the trigger foods were known to develop a threshold for identifying food triggers with good to excellent agreement (Table 3). When both tests were used together, the sensitivity for identifying triggers was improved, with an associated decrease in specificity (Table 4). However, investigators will accept this trade-off for this protocol so that investigators identify as many potential food triggers as possible to optimize the treatment response rate. Moreover, the agreement across all of the tested foods was substantially better than the reported agreement of 13% using traditional skin prick allergy tests. Investigators have confirmed that the lab studies can yield results within 2 weeks, which is a clinically acceptable time frame. In addition, investigators performed cytokine stimulation testing for 14 EoE cases with IL-4, IL-5, and IL-13 but these results did not clearly help to increase the yield for identifying food triggers, so investigators will not pursue this direction further (data not shown).

Table 3: Performance of lymphocyte proliferation testing for identifying food triggers in EoE

| | Nut | Egg | Soy | Wheat | Milk |
|------------------------|-----|-----|-----|-------|------|
| Testing parameters (%) | | | | | |
| Sensitivity | 100 | 63 | 60 | 20 | 45 |
| Specificity | 82 | 75 | 78 | 50 | 75 |
| Agreement | 75 | 71 | 50 | 42 | 47 |

Table 4: Performance of a positive test on either the lymphocyte proliferation or the IgG4 assay for identifying foods

| | Nut | Egg | Soy | Wheat | Milk |

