|------------------------|-----|-----|-----|-------|------|
| Testing parameters (%) | | | | | |
| Sensitivity | 100 | 100 | 75 | 80 | 64 |
| Specificity | 50 | 50 | 45 | 43 | 25 |
| Agreement | 60 | 75 | 53 | 58 | 53 |

These thresholds will be used in this prospective study of allergen-specific immune signature-guided dietary elimination therapy to assess the clinical effectiveness of this technique. Samples may be tested using additional allergens, including but not limited to beef, corn, fish, shellfish, rice, chicken, potato, pork,

legumes, green beans, tomatoes, green peppers, and tree nuts. Results from these additional allergens are for data collection only and will not be used to drive subject diet elimination or communicated to subjects.

2 Study Objectives

Primary Objective: To evaluate prospectively the effectiveness of individualized allergen-specific immune signature-based dietary elimination therapy for EoE.

We hypothesize that at least 75% of patients with active EoE will experience a histologic response following treatment with an individualized dietary regimen based on their own allergen-specific immune signature.

3 Study Design

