After completion of the EGD and/or collection of EGD records and previous biopsies if an EGD was previously completed), and confirmation of eligibility, subjects will be scheduled for a routine care nutrition counseling appointment. Two weeks prior to the routine care nutrition counseling appointment, subjects will begin the dysphagia symptom questionnaire (DSQ). During the routine care nutrition counseling appointment, the subject will receive counseling on which foods to eliminate based on the T-cell and IgG4 results from the research biopsies. Subjects will also receive an allergy skin test during this visit. Results from the allergy skin test will not be used to drive food elimination diet.

Subjects will follow their assigned food elimination diet for 6 weeks. At 6 weeks subjects will be scheduled for a routine care esophagogastroduodenoscopy (EGD) with biopsies for clinical purposes. Two weeks prior to the 6 week EGD subjects will restart the DSQ. Data will be collected from the 6 week EGD but no research specific biopsies will be obtained during that visit. Research specific blood will be taken at this visit. Study participation is complete after completion of the 6 week EGD.

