3.3 Protocol Map

3.4 Study Outcomes

The primary outcome will be histologic response, defined as a post-treatment esophageal eosinophil count of <15 eos/hpf.⁴¹ The esophageal eosinophil counts will be quantified using our previously validated protocol.⁴²

The secondary outcomes will be: 1) change in the absolute esophageal eosinophil count; 2) improvement in the endoscopic appearance, as measured by a validated endoscopy score,⁴³ and 3) improvement in symptoms, as measured by a validated dysphagia symptom score.⁴⁴

4 Subject Selection and Withdrawal

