5.2 Day 1 Visit

Two weeks prior to the day 1 visit, and while the lab performs T-cell and IgG4 signatures testing, subjects will be asked to fill out the Dysphagia Symptom Questionnaire (DSQ). The DSQ is a daily 3-question symptom diary to be completed nightly over a 2 week time period. This can be done on paper or by email.

During the day 1 visit, subjects will be scheduled for a routine care nutrition counseling appointment. During this appointment subjects will be advised how to effectively follow an elimination diet based on the specific triggers identified between Screening and Day 1 using samples obtained for the research study and will undergo allergy skin prick testing as a research procedure. Results from the allergy skin prick testing will not be used to drive the food elimination diet.

Subjects will be instructed to eliminate between 1 and 5 foods (dairy, wheat, egg, soy, and/or nuts) based on results from the T-cell and IgG4 signatures. Subjects will adhere to the elimination diet for 6 weeks

The following procedures will be completed during the day 1 visit

- DSQ (started 2 weeks prior to day 1 visit)
- Current medications
- Adverse events
- Nutrition counseling as per routine care
- Begin 6 week diet elimination therapy
- CRF completion

5.3 6 Week Follow-Up Visit (+/- 7 days)

Two weeks prior to the 6 week follow-up visit, subjects will be asked to fill out the Dysphagia Symptom Questionnaire (DSQ). The DSQ is a daily 3-question symptom diary to be completed nightly over a 2 week time period. This can be done on paper or by email.

After completion of the 6 week food elimination diet, subjects will return to one of the UNC endoscopy centers and undergo repeat EGD for routine care. During the EGD, clinical biopsies will be obtained. No research biopsies are collected for this study during the 6 week follow-up EGD. Follow up blood samples are collected. Subjects will complete the same questionnaires as the screening visit.

The following procedures will be completed during the 6 week follow-up visit

- DSQ (started 2 weeks prior to 6 week follow-up visit)
- Vital Signs
- Questionnaires
- EGD with EREF score and biopsies for pathology, per routine care (no research biopsies are obtained at the 6 week follow-up visit for this study)
- Blood collection
- Adverse events

Study participation is complete after completion of the 6 week follow-up visit.

6 Statistical Plan

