6.1 Sample Size Determination

Because this is a proof-of-principle effectiveness study without a comparison group, there is not a formal sample size calculation. However, we plan to consent and enroll up to 30 subjects with a goal of 20 subjects completing the study to show that 75% (15) have a histologic response to the allergen-specific immune-signature dietary elimination. We feel that this is a robust number of patients to demonstrate a preliminary effect, while also being a realistic number to enroll during this pilot study. In addition, while the 95% CIs around this goal are somewhat wide (47-92%), current allergy testing only has the ability to accurately predict triggers 13% of the time, so even if we are at the lower end of the range, it's still a major clinical step forward in practice.

In the proposed study, we will be performing the first prospective effectiveness study of an allergen-specific immune signature-based individualized dietary elimination regimen in patients with EoE. Because we are conducting what will essentially be a pilot or proof-of-principle study, the data we collect, including response rates and magnitude of response, will directly inform a planned large scale (ie R01) grant application for a randomized study of immune-signature-based elimination versus empiric food elimination.

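### Section 6.1 judges the lower end of a histologic-response interval against a 13% trigger-identification rate, which this trial does not estimate

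*Combined protocol and SAP*

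**What the plan says.** Section 6.1 (Sample Size Determination) states that there is no formal sample size calculation. The plan is to enrol up to 30 subjects, with 20 completing, and to show a histologic response in 15 of them (75%). It gives 47-92% as the 95% CI around that goal and defends the width of the interval on the ground that "current allergy testing only has the ability to accurately predict triggers 13% of the time, so even if we are at the lower end", the result would be a major clinical advance. It adds that the response rates will feed a grant application for a randomized comparison with empiric food elimination.

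The 13% appears twice more, both times in Section 1.2. There an elimination diet based on skin-prick testing "correctly identifies food triggers in only 13%, a rate that is far worse than expected by chance alone". Later in that section the pilot assay results are summarised by saying that "the agreement across all of the tested foods was substantially better than the reported agreement of 13% using traditional skin prick allergy tests".

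The trial's own quantity is set out in two places. Section 2: "We hypothesize that at least 75% of patients with active EoE will experience a histologic response following treatment with an individualized dietary regimen". Section 3.4: "The primary outcome will be histologic response, defined as a post-treatment esophageal eosinophil count of <15 eos/hpf".

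**The concern.** Section 6.1 sets a response rate beside a test-accuracy rate and draws a clinical conclusion from the gap. A response rate answers whether a patient's oesophagus improved on the diet. A trigger-identification rate answers whether the test named the right foods. If the second is not what the trial measures, a value of 47% on the first cannot be called an advance over 13% on the second.

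The 13% is the only figure 6.1 offers for treating a result below 75% as important. As written, a response rate in the high forties could be reported as an improvement on allergy testing. Because these response rates are meant to inform the larger grant application, the reading could be carried into it.

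**Working it through.** **1. The plan's own interval.** Inputs from Section 6.1: x = 15 responders, n = 20 completers, 95% confidence.

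- Exact (Clopper-Pearson): lower = Beta quantile(0.025; x, n−x+1) = Beta quantile(0.025; 15, 6) = 50.9%. Upper = Beta quantile(0.975; x+1, n−x) = Beta quantile(0.975; 16, 5) = 91.3%.
- Wald: 0.75 ± 1.96 × √(0.75 × 0.25 / 20) = 0.75 ± 0.190, or 56.0-94.0%.
- Other methods: Wilson 53.1-88.8; Wilson with continuity correction 50.6-90.4; Wald with continuity correction 53.5-96.5; Agresti-Coull 52.8-89.2; Jeffreys 53.6-89.8.

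None of the seven gives 47-92%. Their lower limits run from 50.6% to 56.0%. For 12/16, which is also 75%, the exact interval is 47.6-92.7% (47-92 if truncated) and Wilson with continuity correction gives 47.4-91.7% (47-92 if rounded). A different denominator is therefore a possible source, but the documents do not confirm it.

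**2. What each percentage counts.**

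| Figure | Where | What it describes |
|---|---|---|
| 75%, CI printed as 47-92% | 2, 3.4, 6.1 | Patients with <15 eos/hpf after the diet |
| 13% | 1.2 (twice), 6.1 | Correct identification of, agreement on, or prediction of food triggers by allergy testing |
| 53-75% | 1.2, Table 4 | Per-food agreement of the combined assay with known triggers |

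Nowhere is the 13% given as a histologic response rate. Its like-for-like counterpart is the Table 4 agreement, which this trial does not re-estimate.

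**3. Whether the design links the two.** Section 1.2 says that current dietary therapy removes many foods empirically and then needs "subsequent reintroduction of single foods, then endoscopy and biopsy to assess for recurrent tissue eosinophilia". In this trial one to five foods are removed together (5.2), and "Study participation is complete after completion of the 6 week EGD". It follows that:

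- A responder who removed several foods does not show which of them mattered. Only a responder who removed a single food would.
- A patient can respond although some removed foods were harmless. Table 4 specificity of 25-50% makes that a real prospect, and Section 1.2 accepts the trade-off. Response says nothing about needless removals.
- Response bears on accuracy only indirectly, through triggers that were missed.
- Skin-prick testing on Day 1 could show which foods each method flags, but without reintroduction it gives no accuracy rate. Section 6.2 plans no analysis of it.

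**4. How low a bar 13% is.** Exact 95% CIs at n = 20:

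| Responders | Rate | 95% CI | Lower limit above 13%? |
|---|---|---|---|
| 6 | 30% | 11.9-54.3% | No |
| 7 | 35% | 15.4-59.2% | Yes |
| 9 | 45% | 23.1-68.5% | Yes |
| 15 | 75% | 50.9-91.3% | Yes |

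The smallest count that excludes 13% is 7, with one-sided exact P(X ≥ 7 given p = 0.13) = 0.010. Seven of 20 is 35/75 = 47% of the hypothesised rate.

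**5. Whether the interval error matters to the comparison.** It does not. The lower limit exceeds 13% by 47 − 13 = 34 points as printed and by 50.9 − 13 = 37.9 points when corrected. Neither difference has a meaning, because the quantities differ.

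**The case against.** The strongest reply is that nothing operational depends on the sentence. The study is a pilot with no formal sample size calculation, Section 6.2 counts responders and applies Wilcoxon tests, and no null or decision rule refers to 13%. That stands, and it limits the point to a minor one. It also means that the 7/20 threshold in the working is an illustration of how little the comparison discriminates, not a rule in the plan.

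A second reply is that 6.1 never claims to estimate trigger accuracy. It can be read as a loose clinical argument: existing tests guide diets badly, so a test-guided diet that helps about half of patients would be useful. That is a fair motive for the trial, but it is not the inference on the page, which derives the clinical advance from the 13%. A diet can work for half of patients because it removes many foods, whatever the accuracy of the test behind it.

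Third, the unit of the 13% (patients, foods or tests) is not stated, and its sources are not available here. That limits what can be said about its denominator. It does not change the fact that every mention describes trigger identification.

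Fourth, the 13% has a proper counterpart in Table 4, so it need not disappear from the document. Agreed: Section 1.2 already makes that comparison and can keep it.

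Finally, the carry-forward risk is only a possibility. The grant is to be informed by response rates, and its comparator is empiric elimination, so 13% has no stated role there.

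**Conclusion.** The concern holds, at minor severity. The conclusion in 6.1 about the lower end of the interval does not follow, because it sets a histologic response rate against a trigger-identification rate that the design cannot estimate. The comparison would be passed by 7 responders in 20, less than half the hypothesised 75%. The printed 47-92% is also not the interval for 15/20; the exact interval is 50.9-91.3%.

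This rests on the documents' own descriptions of the 13%, on 20 completers as planned, and on two-sided 95% limits. The defect lies in the stated interpretation and in one printed interval. The endpoint, the sample size (which rests mainly on feasibility and the 75% goal) and the planned analyses are not affected. The documents give no numeric response rate for empiric elimination, so no replacement benchmark is offered.

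**What to change.** In Section 6.1, delete the comparison with 13% and the conclusion drawn from it. Replace them with:

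> With 20 completers, 15 responders (75%) would give an exact 95% CI of 50.9-91.3%. The trial estimates histologic response; it does not estimate trigger-identification accuracy, because foods are not reintroduced.

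State openly that 50.9-91.3% replaces the printed 47-92%, which 15/20 does not reproduce. Optionally, tabulate the number and identity of foods removed per subject (one to five) beside the response rate, since the trial already generates these data.

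The cost is about two sentences of text, with no change to endpoint, sample size, data collection or the analyses in 6.2. The stated claim becomes less favourable, and 6.1 is left without an external figure for a result below 75%, which would be reported descriptively with its CI.

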6.2 Statistical Methods

To determine the response rate for the primary outcome, the number of subjects with <15 eos/hpf on follow-up endoscopy will be calculated. For secondary outcomes, median eosinophil counts, endoscopy scores, and symptoms scores will be compared before and after treatment with Wilcoxon signed-rank. These will be contextualized by calculating odds ratios and 95% confidence intervals where appropriate, so as not to

over-rely on p values alone. Patients who drop out or who have incomplete data for the outcomes will be excluded from analysis. Because this study's outcomes are determined after the treatment period and follow-up endoscopy, a subject must complete this end of treatment evaluation for us to be able to include their data in the analysis. We do not feel that selection bias would impact the analysis if there are incomplete data due to drop out. We are not performing a comparative analysis between groups, so drop out would not be dependent on different treatments administered in different study arms. In addition, in our experience with previous clinical studies of EoE, dropout rates have been quite low.

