3.1 General Design

This is a prospective single center clinical trial of allergen-specific immune signature-guided dietary elimination therapy to assess the clinical effectiveness of this technique.

Potential subjects will be approached regarding the study. If eligible and interested, then informed consent will be obtained and they will be enrolled in the study. If the subject has had an esophagogastroduodenoscopy (EGD) at UNC within 3 months since enrollment, clinical biopsies from the EGD show active EoE and the subject continues to meet consensus guidelines for active EoE, and research biopsies were taken during that EGD that can be used for this study, then the subject will complete questionnaires and a blood draw only. The blood draw may be abbreviated if the subject had research blood drawn during the same recent EGD that can be used in this study.

If subjects have not had an EGD with biopsies at UNC within 3 months prior to enrollment, then they will complete questionnaires, a blood draw, and be scheduled to receive a routine care esophagogastroduodenoscopy (EGD) at UNC facilities with clinical and research biopsies. However, in some cases, samples that were obtained prior to this time frame can be used, as long as the samples were obtained when the EoE was active and there were no major changes in clinical status.

During the routine care endoscopy, clinical biopsies will be taken for routine care purposes, and additional research biopsies will be collected for research purposes for diet elimination testing and to be stored for future research studies from the distal, mid, and proximal esophagus. Blood will also be collected during this visit, and questionnaires completed. If research biopsies are unable to be obtained during this EGD the subject will no longer continue in the study and will be considered a screen fail. If pathology from routine care biopsies does not confirm a diagnosis of active EoE, then the subject will no longer continue in the study and will be considered a screen fail. If subjects have had an EGD with clinical and research biopsies within 3 months prior to enrollment, then research biopsies taken during that EGD will be used for this study. As noted above, in some cases, samples that were obtained prior to this time frame can be used, as long as the samples were obtained when the EoE was active and there were no major changes in clinical status.

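### Section 6.2 pairs Wilcoxon signed-rank tests of counts and scores with odds ratios, which do not follow from them, so the size of the paired change has no prespecified interval

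*Combined protocol and SAP*

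**What the plan says.** Section 6.2 Statistical Methods has three relevant elements; the Statistical Methodology row of the Study Summary repeats them.

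- **Primary outcome.** Responders at the follow-up endoscopy are counted. Section 3.4 gives the outcome as "histologic response, defined as a post-treatment esophageal eosinophil count of <15 eos/hpf", so it is defined only after treatment.
- **Secondary outcomes.** Median eosinophil counts, endoscopy scores and symptom scores are compared before and after treatment with the Wilcoxon signed-rank test.
- **Effect measure.** The next sentence says these will be put in context by "calculating odds ratios and 95% confidence intervals where appropriate", with the stated aim of not leaning on p values alone. Its opening pronoun refers most naturally to the paired comparisons just described.

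There is one arm. Section 6.1 states: "Because this is a proof-of-principle effectiveness study without a comparison group, there is not a formal sample size calculation". Section 6.2 adds: "We are not performing a comparative analysis between groups". The target in section 6.1 is "a goal of 20 subjects completing the study to show that 75% (15) have a histologic response". The same section says that response rates and the size of response will feed a grant application for a randomized study.

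**The concern.** A signed-rank test works on within-subject differences in a count or score. The effect estimate that belongs with it is a location of those differences, in eosinophils per high-power field or in score points. An odds ratio needs a binary outcome, and either two groups or two occasions to contrast. The plan supplies neither a cut-point nor a contrast for any secondary outcome.

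The sentence exists to give readers a magnitude with its uncertainty. The measure it names cannot do that without a further decision that the plan leaves open. The analyst must either drop the odds ratio, leaving p values and separate medians, or dichotomise a score after seeing the data. With about 20 completers, the choice of cut-point could change the result materially. Because the size of response is meant to inform the next trial, an interval for the change is worth prespecifying.

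**Working it through.** **Inputs.** 20 completers and 15 responders as the goal, and no comparison group (section 6.1). Three paired secondary outcomes tested by signed-rank (sections 3.4 and 6.2). Response defined as fewer than 15 eos/hpf after treatment (section 3.4). Subjects without confirmed active disease leave the study: "If pathology from routine care biopsies does not confirm a diagnosis of active EoE, then the subject will no longer continue in the study" (section 3.1).

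**The plan's own figure.** The only computed interval is 47 to 92% around the 75% target (section 6.1). For 15/20 the usual methods give:

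- Clopper-Pearson 50.9 to 91.3%
- Wilson 53.1 to 88.8%
- Wilson with continuity correction 50.6 to 90.4%
- Wald 56.0 to 94.0%

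None reproduces 47 to 92%. Wilson with continuity correction at 12/16 gives 47.4 to 91.7%, which would round to it. This is a separate matter, and nothing below depends on it.

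**Step 1: secondary outcomes.** For subject i the signed-rank test uses d_i = (after) − (before). It ranks the absolute differences and sums the ranks by sign. No 2×2 table arises, so no odds ratio follows. Getting one needs a responder definition for each score, or an exposure to relate to response, and sections 3.4 and 6.2 give neither. The matching estimate is the Hodges-Lehmann one: the median of all averages (d_i + d_j)/2 with i ≤ j. With n completers there are n(n + 1)/2 of these, so 210 averages at n = 20. Its 95% CI comes from inverting the same test. It cannot be evaluated here because the documents give no change data.

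**Step 2: could the one defined binary outcome supply the odds ratio?** The plan does not propose this; the step only tests whether it would rescue the choice. In a before/after table let b be the subjects who become responders and c those who cease to be. The paired odds ratio is b/c. Assume every subject is at or above 15 eos/hpf at baseline. Then c = 0 whatever the number of responders, and at the target b = 15.

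- Point estimate: b/c with b = 15 and c = 0, not finite.
- Exact 95% interval: the lower limit p for the discordant proportion is 0.025 raised to the power 1/b, which is 0.782; as odds, p/(1 − p) is 0.782 divided by 0.218, about 3.6. There is no upper limit.
- Adding 0.5 to each discordant cell: 15.5 divided by 0.5 gives 31. The standard error SE of its logarithm is √(1/b + 1/c) with b = 15.5 and c = 0.5, and exp(ln OR ± z × SE) with z = 1.96 runs from 1.9 to 518.
- Adding 0.5 and ignoring the pairing: the product of 15.5 and 20.5, divided by the product of 5.5 and 0.5, gives 116, with interval 5.9 to 2251.

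The two corrected values, 31 and 116, come from the same data, so the reported figure would depend mainly on the device used to avoid the zero.

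**Step 3: what fits the primary outcome.** A proportion with an exact interval: 15/20 is 75%, Clopper-Pearson 50.9 to 91.3%.

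**The case against.** The best defence is that the sentence is conditional. Its qualifier lets the analyst omit an odds ratio wherever it does not fit, and the reference to confidence intervals can be read as covering other estimates too. Section 3.4 also words two secondary outcomes as improvement. Improved versus worsened is a paired binary contrast with an ordinary matched odds ratio, and eligibility creates no structural zero for it. Before and after medians would be reported in any case, and section 6.1 already shows an interval around the target response rate.

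Much of this stands, and it rules out three stronger readings.

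- A reader might infer that the plan computes an odds ratio for histologic response and would report an infinite one. The text attaches odds ratios to the secondary outcomes and only counts responders. Even for that calculation, an exact lower limit exists.
- A reader might infer that no outcome in this design could carry an odds ratio. That is too absolute: improvement versus worsening could, and so could a baseline predictor of response.
- A reader might infer that the secondary outcomes would have no estimate of size. The medians are estimates; what is missing is an interval for the paired change.

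The defence does not supply a definition. The plan sets no improvement threshold, no rule for unchanged scores and no predictor analysis. If the intervals are meant for something other than odds ratios, it does not say what. The qualifier therefore points to no planned analysis.

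**Conclusion.** The point holds as a mismatch between test and effect measure for the three secondary outcomes. As written, the plan secures medians and p values but no prespecified interval for the size of the paired change, and it leaves room for a cut-point chosen after the data are seen. Histologic response offers no way out. That part rests on an inference: zero baseline responders follows from the active-disease requirement, but the documents cite consensus guidelines and state no baseline eos/hpf threshold. If some subjects were below 15 at baseline, the paired odds ratio would be finite only if at least one of them was no longer a responder at follow-up.

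The size is modest. Reporting of secondary results is affected; the primary response rate and the sample size are not.

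**What to change.** In section 6.2 and in the Statistical Methodology row of the Study Summary, replace the odds ratios with an estimate of the paired change and its 95% CI for eosinophil count, endoscopy score and symptom score. The Hodges-Lehmann estimate is a natural choice because it matches the signed-rank test; a median within-subject change with a suitable interval would also serve. In the same sentence, state that the response proportion will be reported with an exact 95% CI. If an odds ratio is still wanted, for instance for improvement versus worsening, define the binary outcome and the handling of unchanged scores before the data are examined.

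The cost is one sentence in two places. The estimates are standard software output and need no new data and no change to study conduct.
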